Exclusion Criteria for Youths: Concurrent participation in any other research in which treatment adherence or glycemic control are study outcomes; Daily oral glucocorticoid treatment; Significant developmental delay (self-contained special education; retention in 2 or more grades); Inability to read/comprehend study questionnaires and decision aids in English; Treatment for a coincident medical condition that, in the opinion of the treating physician, represents a contraindication to study participation.

Inclusion Criteria for Parents: Primary diabetes caregiver of index child; Anticipates continued medical care for T1D at Nemours or the Barbara Davis Center for subsequent year; capable of participating in conversations during medical visits; routinely accompanies child for diabetes care at Nemours or the Barbara Davis Center.

Exclusion Criteria for Parents: Inability to read/comprehend study questionnaires and decision aids in English; Child living in a temporary placement such as foster care or juvenile detention center; Evidence of frequent changes in the adolescent's household or living arrangements.

Recruitment, Parental Permission and Adolescent Assent: The study will be approved by a Nemours IRB before recruitment begins. All Nemours health care providers who see patients for management of type 1 diabetes, and who may be in a position to evaluate and prepare candidates for incorporation of either CSII or CGM into their care plans, will receive an initial e-mail describing the study and announcing the opening of enrollment. HCPs will be provided with a link to the web-based decision aids for their inspection. A total of 13 Nemours pediatric endocrinologists and diabetes educators provided information and feedback that has been

incorporated into the decision aids as they were being developed.

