Randomization will occur at the level of patients rather than by sites or clinicians since it is the patient's behavior that is most proximal to the primary endpoints and since randomizing at the level of site or clinician runs the risk of baseline differences between groups on key clinical practices or clinician communication style. Randomization will be stratified by enrolling site so that each site randomizes a similar number of participants to UCP and SMDM. The Senior Research Coordinator in Jacksonville will compile randomization lists for each site and will manage the randomization process for all sites. We considered including an "attention placebo" control group, but decided against this due to the brief, highly structured SMDM intervention (A few extra hours over 2-4 weeks), relatively long follow-up, and difficulty in defining the precise activities that would constitute a meaningful and appropriate attention control that is not seen as transparent by the participants. The extra attention to the SMDM group is in fact the independent variable, consisting of a well-defined educational intervention. Given the limited number of eligible patients, reaching recruitment objectives for a 3-group design would be more difficult and expensive than with a 2-group design. Additional discussion of this issue appears in the Limitations section.

The decision aids developed for this study have received iterative review and feedback by a diverse group of patients and parents who have previously made decisions about CSII or CGM, by multiple Nemours HCPs who care for such patients, by two general pediatricians who are SMDM experts (Drs. [name] and [name]) and by two pediatric endocrinologists ([name], one of our external consultants and [name] who is employed part time by KidsHealth). In addition, the KidsHealth production team reflects substantial expertise in development of health care communications that are designed to harmonize with the developmental characteristics and priorities of adolescents and with the typical concerns and perspectives of parents. We believe that this combined input has yielded very high quality decision aids that are exceptionally engaging, informative and interactive guides that will help adolescent patients and their parents reach better decisions about CSII and CGM that are likely to facilitate adolescents' engagement with whichever treatment alternative they ultimately select.

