SMDM by definition seeks to reflect the perspectives of youths, parents, and HCPs and that is how the proposed intervention has been designed. The visits with the Diabetes Educator (DE) and use of the decision aids are designed to equip parents and youth to have more meaningful and productive discussions with HCPs about the merits of the treatment option of interest than they might achieve without the SMDM intervention. This enhanced communication, along with personal ownership of the decision, is expected to help adolescents and parents make an important treatment decision more effectively with their HCP. Hence, each SMDM patient will collaborate with their diabetes HCP and DE to reach an informed decision about CSII or CGM. We will document details of each participant's educational experiences during the decision making process as a means of verifying the integrity of the experimental manipulation (See Appendix). Each parent/adolescent dyad randomized to SMDM will have an initial orientation visit with a trained research staff member (either in person or via a scheduled phone conference), consisting of an introduction to SMDM and to the structure, content and operation of the decision aid to be used by that family. The parent and adolescent will be asked to use the decision aid over the subsequent 2-4 weeks and to come prepared to discuss with the DE at the second visit each of the discussion points that appear throughout the decision aid, as well as any other questions or comments they might wish to address. At the second visit, the DE will prepare a summary of the family's SMDM experience that will be sent to the adolescent's T1D HCP for discussion at their next clinic visit and to the research team as a process measure of each family's SMDM experience. Each HCP will be provided with a brief orientation regarding the structure of the SMDM intervention and they will be invited to inspect/use each of the two decision aids at their convenience.

UCP Intervention: The UCP intervention will consist of the education and consultation procedures currently employed at each of the participating sites for patients and families who are considered by the health care team to be suitable candidates for either CSII or CGM. There is some variability across sites and physicians in

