A Diabetes Educator (DE) at each Nemours site and the Barbara Davis Center will conduct face to face interactions with SMDM participants using the web-formatted decision aid as the framework for delivery of the SMDM intervention. Each patient, parent and any other supportive persons they wish to invite will meet with the DE after they have completed use of the decision aid (~2-4 weeks) during which the pertinent decision aid will be reviewed. Supportive persons identified by the parent or youth will be encouraged to view and use the decision aids along with the enrolled adolescent or parent. The DE will assist participants in identifying any remaining uncertainties they may have about the decision and coaching about how to bring these issues to a clinic visit with the referring HCP. A written summary of the patient's and parent's perspectives during the SMDM sessions, agreement between their perspectives and their remaining issues will be drafted by the DE and forwarded to the referring HCP (See Appendix) and to the research team as an SMDM process measure for each family. The SMDM intervention will conclude with a clinic visit with the referring HCP who will discuss the participants' remaining questions and perspectives about the information they have received and help them to arrive at a consensus decision about the medical option under consideration, including the possibility of deferring the decision to a later date. Those patients who become candidates for more than one of the options of interest during the study will repeat these interactions for each decision being considered

Practical considerations: The process of becoming a candidate for either CSII or CGM may be complicated in several ways that may make it more difficult to evaluate the specific contributions of the SMDM intervention that is planned. Below, we have listed specific complicating factors that can be anticipated and planned methods for addressing each of them:

Complicating Issue	Planned Resolution
Delay between decision to accept CSII or CGM and its actual receipt by the patient and family due to insurance denials, etc.	Questionnaire administration will occur as outlined in the measurement schedule, but collection of CSII or CGM download data will not commence until the device is received and activated.

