B.6. Limitations A potential limitation of the proposed work is that we have not included a comparison group that provides a control for the additional professional attention that will be afforded to the SMDM families relative to the UCP families. Our primary justification for this is that SMDM is the independent variable in this study design and thus it is legitimate that the experimental and control groups differ along this one dimension. The DE's activities in implementing the SMDM intervention are highly structured and time-limited and are based on use of very detailed decision aids supplemented by very specific interactions. The current educational and decision-making practices utilized at the various performance sites for transitions to CSII or CGM represent the most appropriate standard of comparison since these methods likely represent typical practice variations at centers that commonly offer these diabetes management alternatives. Adding a control condition that includes delivery of equal frequency and duration of professional contact as does our SMDM condition would be difficult to define or justify, would run a high risk of appearing artificial, tangential and transparent to participants and would be unlikely to mirror clinical reality anywhere. Extensive research has shown that family management of T1D is quite resistant to improvement in response to carefully designed, intensive behavioral interventions.^{1, 16-22, 26, 100-103} The presumption that slight differences in the type and amount of professional attention offered to families in an attention control condition versus usual care would yield markedly different effects on diabetes outcomes is very unrealistic when viewed from this perspective. Incorporating a third condition into our study would either require a larger total sample of participants (which would be financially and logistically impractical) or impede the statistical power of the study due to smaller sample size per cell (which would be unacceptable scientifically). Finally, randomizing 67% of participants to study conditions that are expected to be less effective is less acceptable ethically than a randomization process that gives every participant a 50% chance of being assigned to the presumably more potent condition. A second limitation is that the applicability of the SMDM intervention format to situations in which youth, parents and HCPs are *collaborating* in medical decision making is unknown at this time. While SMDM interventions for adult patients have typically encouraged the involvement of the patient's significant others in decision making, it is usually clear that the final decision rests with the adult patient and HCP. This may be less clear in pediatrics, but, at a minimum, the SMDM intervention will provide youth with a safe, structured vehicle for exploring and articulating their preferences, goals, apprehensions and expectations regarding the specific medical decisions under consideration and this process should enhance the likelihood of positive outcomes regardless of the ultimate decision that is made since excellent diabetes outcomes are still possible with standard care even if the treatment option being considered is rejected or deferred.

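### Clinicians who counsel both arms may inspect and use the decision aids with no limit to SMDM families, so aid content can reach clinic-recruited UCP families

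*Combined protocol and SAP*

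**What the plan says.** **Unit of randomization.** Section B2 states: "Randomization will occur at the level of patients rather than by sites or clinicians". Its reasons are that the patient's behavior lies closest to the primary endpoints and that "randomizing at the level of site or clinician runs the risk of baseline differences between groups on key clinical practices or clinician communication style". It adds: "Randomization will be stratified by enrolling site so that each site randomizes a similar number of participants to UCP and SMDM". Both arms are therefore present at every site.

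**Provider access.** Section B.1 (Recruitment) describes an e-mail to Nemours type 1 diabetes providers when enrollment opens and says "HCPs will be provided with a link to the web-based decision aids for their inspection". Section B2 adds a short orientation to SMDM for each provider and says "they will be invited to inspect/use each of the two decision aids at their convenience". Neither place ties use to a patient's arm or gives an end date. Specific Aim 2 and B2 require a registered username and password to open the aids.

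**Delivery.** "A Diabetes Educator (DE) at each Nemours site and the Barbara Davis Center will conduct face to face interactions with SMDM participants". The educator's written summary of each SMDM family goes to that family's provider.

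**Control arm.** UCP is the sites' existing education and consultation. Section B.6 says: "The current educational and decision-making practices utilized at the various performance sites for transitions to CSII or CGM represent the most appropriate standard of comparison". B.6 discusses the lack of an attention control and the three-way nature of pediatric decisions. It does not mention carry-over between arms.

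**Recording.** B2 promises to document each participant's educational experiences as a check on the integrity of the manipulation, and to have UCP dyads reconstruct their information sources. B.3 gives UCP families a 10-item process form, intended mainly for description. B.3 limits decision-aid utilization tracking to SMDM participants.

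**The concern.** A clinician who has been oriented to SMDM, has a login to both aids and receives educator summaries on SMDM families will also see UCP families facing the same choice. No sentence tells clinicians or educators to keep the aids, or the summaries, out of UCP visits. What they can pass on (evidence summaries, the burden of each device, prompts about values and barriers) overlaps with what B2 lists as the added content of SMDM.

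The most exposed endpoint is the Test of CSII or CGM Knowledge. B.3 says it is based on the content of the aids, and B.5 lists it as primary. A clinician who repeats aid content to a UCP family could raise that family's score directly.

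If this happens, the observed difference understates the effect of SMDM against true usual practice. A null result would then be hard to separate from a control arm that had taken up part of the intervention.

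**Working it through.** **1. Is there a route from the aids to UCP families?**

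- Shared clinicians: this follows directly from patient-level randomization stratified by site (B2).
- Access by those clinicians: given in B.1 and B2, behind a login, with no limit by arm.
- A rule against use with UCP families: none found in B.1, B2, B.3 or B.6.
- Shared educators: possible but not stated. The budget justification counts educators among clinic staff and funds extra time per SMDM family. The SMDM version of the process form in Appendix 2 lists a teaching session with a diabetes educator among activities the family would have had outside the study. So educators teach in usual care, and nothing separates the two roles.
- Exception: under Recruitment Plan C the family's physician has no role beyond being informed and supplying HbA1c results, and no educator summary is completed.

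**2. Would the plan detect it?** The visible items of the process form (Appendix 2) ask about internet, books and workshops, talking with others, and the work involved. None names the study aids. The first rows of the UCP version were not in the text reviewed. The SMDM version has eight activity rows; with the outcome and satisfaction questions this fits the stated 10 items, which suggests, without proving, that no such item exists.

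**3. The plan's own power figure.** Inputs from B.5: 166 enrolled, 10% attrition (166 × 0.9 = 149.4, taken as 150, or 75 per arm), effect about 0.4 SD, two-sided α = 0.05, stated power 0.87.

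Power ≈ Φ(δ√(n/2) − 1.96) = Φ(0.4 × √37.5 − 1.96) = Φ(0.49) = 0.688; the t-test gives 0.682. The stated 0.87 does not reproduce. At 75 per arm it corresponds to an effect of 0.504 SD. That is a separate matter, so both starting points are carried forward.

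**4. Dilution.** Let c be the average share of the SMDM effect that UCP families acquire. The documents give no value, so c is an **assumption**. Observed effect = δ(1 − c); the sample size needed for fixed power grows by 1/(1 − c)².

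| c (assumed) | Observed effect, from 0.4 SD | Power, t-test, 75 per arm | Power if the stated 0.87 is accepted (0.504 SD, normal approximation) | Sample size factor |
|---|---|---|---|---|
| 0 | 0.40 | 0.682 | 0.870 | 1.00 |
| 10% | 0.36 | 0.591 | 0.793 | 1.23 |
| 20% | 0.32 | 0.495 | 0.695 | 1.56 |
| 30% | 0.28 | 0.399 | 0.579 | 2.04 |

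Because c averages over all UCP families, Plan C families with almost no carry-over pull it down.

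**The case against.** **The access is controlled.** There is no open link: a login must be issued, educators register SMDM families, and the aids are listed only under SMDM. This stands. UCP families are not given access, so what could leak is content and counselling style through a provider.

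**A clinician who has viewed a website does not deliver SMDM.** The package is two to four weeks of family use, values clarification, narratives, an educator review and a written summary, designed to exceed what a busy practice can offer. This also stands. A reader might infer that UCP is bound to drift toward SMDM and that every endpoint is biased. The documents show an unguarded route, not that it is used or how far it reaches.

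**Exposure is recorded.** A reader might infer that contamination could never be detected. B2 and B.3 do collect UCP families' information sources. The defensible statement is narrower: no visible item names the study aids.

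**Shared educators are an inference.** This stands. B2 gives the orientation to research staff, and the replication section reports more use of private pump educators in the Delaware Valley, so site educators need not do all UCP teaching.

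**Patient-level randomization was reasoned.** It was, and this point does not ask to change it. But the reasons given weigh baseline balance and closeness to the endpoint, not carry-over.

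**The remedy is imperfect.** A family often cannot tell whether counselling drew on the aids, and a fragment is not full SMDM, so a complier-average estimate would rest on weak ground. Nor can a rule undo what the 13 Nemours clinicians and educators who contributed to the aids already know. Both limits are accepted: hence a matching question to the provider, and an exploratory role at most for any adjusted estimate.

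**Conclusion.** The point holds as a gap in the plan. Clinicians who counsel both arms are invited to use the aids without restriction by arm, and no rule, visible exposure item or stated limitation covers carry-over to UCP. The expected direction is toward a smaller SMDM-UCP difference, most directly on the Knowledge Test. It applies to clinic-recruited families and hardly at all to Plan C.

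The size is unknown. Under assumed average carry-over of 10% to 30%, power for a true 0.4 SD falls from 0.68 to between 0.59 and 0.40, or from the stated 0.87 to between 0.79 and 0.58. These figures illustrate sensitivity; they are not estimates, and they assume the same proportional dilution on each endpoint. The power statement in B.5 allows nothing for dilution. The change is worth making because it is cheap, and exposure not asked about during follow-up cannot be recovered reliably later.

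**What to change.** 1. **B.1 and B2:** replace the open-ended invitation with provider access for orientation and for work with SMDM families, through individual logged accounts. The platform already time-stamps use.
2. **B2:** state that providers and educators do not show or share the aids or the SMDM summaries with UCP families during follow-up, and that usual counselling is otherwise unchanged.
3. **B.3 and Appendix 2:** add one item to the UCP process form on exposure to the study aids, and a matching question for the provider.
4. **B.5:** report the UCP exposure rate beside the intention-to-treat result. Label any contamination-adjusted estimate exploratory.
5. **B.6:** name contamination as a limitation, including the prior knowledge of staff who helped develop the aids, and say whether the educators delivering SMDM also teach UCP families.

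The cost is account settings, one form item, one provider question and a short site instruction. The downside is that providers have less free access to the aids. Randomization and sample size stay as they are.
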